### 3 OBJECTIVES AND ENDPOINTS

OBJECTIVES	ENDPOINTS	JUSTIFICATION FOR ENDPOINTS
Primary		

The primary objective of the current study is to determine the acute effects of cannabis consumption at rest and during exercise on the human cardiovascular system, with particular focus on the influence of method of consumption (smoking vs. vaporizing), and cannabinoid composition (THC vs. CBD).
	
The primary endpoints will be measures of arterial stiffness, endothelial function, muscle sympathetic nerve activity, and cardiac function.
 
Arterial stiffness and endothelial function will be assessed via carotid-femoral pulse wave velocity and brachial artery flow-mediated dilation.
 
Muscle sympathetic nerve activity (MSNA), or microneurography, will be characterized using indices of sympathetic outflow, such as burst incidence and burst frequency.
 
Cardiac function will be assessed using echocardiography. Primary endpoints will be measures of systolic function, diastolic function, and tissue mechanics. These measures include but are not limited to ejection fraction, E/A ratio, myocardial twist, and myocardial strain.
	
Carotid-femoral pulse wave velocity has been chosen as a primary endpoint as it has been shown that cigarette smoking, which is not dissimilar to cannabis smoking in many ways, results in arterial stiffening both acutely and chronically. Furthermore, the relationship between pulse wave velocity and risk of cardiovascular events has been well documented. Previous research has identified that a 1SD increase in pulse wave velocity is correlated with a 16-20% increase in risk for cardiovascular events.
 
Similar to pulse wave velocity, brachial artery flow-mediated dilation has been shown to have predictive value in determining risk of cardiovascular events in healthy subjects.
 
Microneurography (MSNA) will allow recording of the electrical activity of sympathetic nerves. This technique provides insight into the autonomic control of the cardiovascular system. This technique will further allow exploration of the mechanisms underlying other primary outcomes. Burst incidence and burst frequency are commonly reported measures of muscle sympathetic nerve activity.

OBJECTIVES	ENDPOINTS	JUSTIFICATION FOR ENDPOINTS

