## 4 STUDY DESIGN

### 4.1 OVERALL DESIGN

The study will use a randomized cross-over design. It will be structured by division into two phases. Both phases will examine the acute cardiovascular response to cannabis consumption,

both at rest and during exercise. *Phase I* will examine if and how this response differs whether cannabis is smoked or vaporized. *Phase II* will examine how this response is influenced by cannabinoid concentration within inhaled cannabis. Phase II of the current study will use a single-blind design, with participants being unaware of the relative cannabinoid concentrations of the cannabis they consume. Cannabis will be inhaled using methods of smoking (phase I only) or vaporization (phase I and II). Each experimental study visit (study visits 2-9), 100mg of cannabis will be consumed via one of the two aforementioned methods of inhalation, followed by a subsequent rest period, or by 20 minutes of exercise. Primary endpoints will be examined pre- and post-consumption each visit (with the exception of muscle sympathetic nerve activity, which will only be performed on a single study visit), while secondary endpoints will be recorded during exercise.

Each phase of the study will require participants to complete an introductory and control visit, as well as 4 experimental study visits, where cannabis inhaled under alternating conditions (phase I: smoking vs. vaporizing high THC cannabis, phase II: high CBD cannabis vs. high THC cannabis) followed by exercise, or a time-matched rest period. The order in which these visits will occur will be randomized, and individualized for each participant. A within-subjects design will be utilized, so that each participant completes each condition. High THC cannabis used will be the cannabis strain “Rex”, while the high CBD strain will be “Kalea”. The dose size and strength will not be altered throughout the course of the study.

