## 8 STUDY ASSESSMENTS AND PROCEDURES

### 8.1 EFFICACY ASSESSMENTS

Participants will be screened for eligibility using two separate screening procedures during the introductory visit. The first screening procedure will be an investigator generated eligibility questionnaire. This questionnaire will evaluate whether the participant fits inclusion criteria and does not meet any exclusion criteria. The second screening tool will be the PARQ+, a validated questionnaire designed to determine whether participants are fit to safely exercise. The PARQ+ may determine that a participant requires clearance from their physician. If they do not obtain a signed doctor's note, they will not be eligible to participate. All screening procedures will occur during the introductory visit, and within one week of the exercise control visit. Additionally, at the start of each study visit participants will be asked if there have been any changes to their health status, or prescription medication status.

Efficacy assessments of primary objectives are as follows:

- Arterial stiffness will be assessed before and after cannabis consumption with and without subsequent exercise under each condition, during each study visit. Carotid-femoral pulse wave velocity will be used to determine arterial stiffness. Carotid-femoral pulse wave velocity will be measured by placing a tonometer probe at the site of the carotid and femoral pulse. Pulse waveforms will be juxtaposed against a lead-II electrocardiogram to determine pulse wave velocity.
- Endothelial function will be characterized before and after cannabis consumption with and without exercise under each condition during each study visit. Endothelial function will be measured using brachial artery reactive hyperemic flow-mediated dilation. The brachial artery will be imaged using a General Electric Vivid-i ultrasound system. After 1 minute of imaging, a tourniquet placed on the antecubital fossa will be inflated to 220mmHg for a period of 5 minutes will imaging continues. After this period 3 minutes of ultrasound imaging will be recorded to assess the vasodilatory response to occlusion. The relative (%) change in arterial diameter following release of the tourniquet will be the primary endpoint.

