- Muscle sympathetic nerve activity will only be performed before and after vaporizing of high THC cannabis. Microneurography will be performed by inserting a tungsten microelectrode into the peroneal nerve. Upon identification of a sympathetic nerve

bundle, baseline activity will be recorded for a maximum of 10 minutes. Participants will then follow the standard smoking protocol, while sympathetic activity is recorded during the rest period.

- Cardiac function will be assessed using echocardiography. Echocardiography will be performed prior to exercise during the exercise control visit, and will be performed after consumption of cannabis on each study visit. Ejection fraction, E/A ratio, myocardial twist, and myocardial strain have all been chosen as these are standard measures for evaluating respective aspects of cardiac function. The heart will be viewed via the parasternal and apical imaging windows, and will be imaged using the Vivid-I ultrasound system.

Efficacy assessments of secondary objectives are as follows:

- Blood pressure, heart rate, and myocardial oxygen demand will be determined using a Finapres device which measures beat-to-beat heart rate and blood pressure using a finger cuff. The product of these two endpoints will represent the rate-pressure product, an indicator of myocardial oxygen demand. These outcomes will be assessed in the 20-minute period following cannabis consumption during each study visit. Therefore, recordings will take place at rest and during exercise depending on the given study visit.
- Indirect calorimetry will be performed during all exercise bouts, and will be used to evaluate oxygen consumption and other cardio-respiratory measures such as respiratory exchange ratio, minute ventilation, and caloric expenditure. Participants will be instrumented prior to each exercise bout, and measurement will only take place during the exercise bout.
- Participants will also be asked to provide ratings of perceived exertion every 2 minutes during each exercise bout. Ratings will be collected using the 6-20 Borg scale of perceived exertion.
- Exercise performance will be quantified by numerous endpoints such as average power output, and total work completed in the allotted exercise period (20 minutes). These outcomes will be assessed using the manufacturer software provided with the cycle ergometer that will be used in all exercise bouts.

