## 9 STATISTICAL CONSIDERATIONS

### 9.1 STATISTICAL HYPOTHESES

- Primary Efficacy Endpoint(s):
  1. Pulse Wave Velocity will be increased following exercise, smoking high THC cannabis, and vaporizing high THC cannabis relative to resting baseline; effects of cannabis consumption and exercise are likely to be additive. Vaporizing high CBD cannabis will not increase pulse wave velocity.
  2. Percent flow mediated dilation will be decreased following exercise and smoking high THC cannabis; effects are likely to be additive. Vaporizing both high THC and high CBD cannabis will not decrease percent flow mediated dilation.
  3. Ejection fraction will be decreased following smoking and vaporizing high THC cannabis. Exercise and vaporization of high CBD cannabis will not be associated with reductions in ejection fraction.
  4. E/A Ratio will be decreased following high THC cannabis smoking only.
  5. Myocardial strain will be decreased following high THC cannabis smoking and vaporizing only.
  6. Myocardial twist will be decreased following high THC cannabis smoking and vaporizing only.
  7. Burst Frequency will be increased following high THC cannabis only.
  8. Burst Incidence will be increased following high THC cannabis only.

- Secondary Efficacy Endpoint(s):
  1. Systolic Blood Pressure will be increased following cannabis consumption and will be decreased following all bouts of exercise.
  2. Diastolic blood pressure will be unchanged under all conditions
  3. Heart rate will be increased following cannabis consumption and exercise.
  4. Stroke volume will be increased with exercise, and will be reduced following cannabis consumptions. These competing effects will result in an attenuation of increases in stroke volume when exercise is preceded by cannabis consumption.
  5. Cardiac output will be unchanged under all conditions
  6. Work completed will be reduced when preceded by cannabis consumption of all forms
  7. Average power output will be reduced when preceded by cannabis consumption of all forms
  8. Oxygen consumption will be reduced when exercise is preceded by consumption of high THC cannabis
  9. Rating of Perceived Exertion will be increased following consumption of high THC cannabis
  10. Rate-pressure product will be increased during exercise, when the bout is preceded by cannabis consumption.

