## 9.2 SAMPLE SIZE DETERMINATION

In accordance with our power calculation, 15 participants are required to have a power of at least 0.8 with an alpha of 0.05, for expected changes in measures of endothelial function (pilot work, change in FMD in response to exercise pre =  $4.8 \pm 2.5$  %, post =  $2.7 \pm 1.7$ %) (FMD in rats in response to cannabis smoke, pre =  $7.5 \pm 2.5$ %, post =  $2.4 \pm 1.4$  %), artery stiffness (pilot work, change in PWV pre =  $7.4 \pm 1.3$  m/s, post (at rest) =  $6.0 \pm 1.3$  m/s) and cardiac function (pilot work, peak longitudinal strain: pre =  $-18.3 \pm 1.2$  %, post =  $-17.0 \pm 1.9$  %), therefore we will recruit 20 participants in each phase of the study to account for potential dropout.

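### Protocol 8.1 lists no pre-cannabis echocardiogram, contradicting 4.1, and no post-exercise control scan, which 9.1 and 9.4 need

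*Protocol*

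**What the plan says.** Section 3 makes the echocardiographic measures primary: "Cardiac function will be assessed using echocardiography. Primary endpoints will be measures of systolic function, diastolic function, and tissue mechanics". The named measures are ejection fraction, E/A ratio, twist and strain.

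Section 4.1 sets the timing rule for primary endpoints: "Primary endpoints will be examined pre- and post-consumption each visit (with the exception of muscle sympathetic nerve activity", which is recorded at a single visit.

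Section 8.1 then gives the timing endpoint by endpoint:

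- Pulse wave velocity: "Arterial stiffness will be assessed before and after cannabis consumption with and without subsequent exercise under each condition, during each study visit".
- Flow-mediated dilation: "Endothelial function will be characterized before and after cannabis consumption with and without exercise under each condition during each study visit".
- Echocardiography: "Echocardiography will be performed prior to exercise during the exercise control visit, and will be performed after consumption of cannabis on each study visit".

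The Schedule of Activities marks echocardiography at Visits 1 to 9 with no timing within the visit.

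On exercise without cannabis, hypothesis 3 in 9.1 states: "Exercise and vaporization of high CBD cannabis will not be associated with reductions in ejection fraction". Section 9.4.1 lists exercise alone as a condition to be compared on the primary endpoints in both phases. Section 9.4.2 says primary endpoints are measured again following every intervention given at a visit. The SAP repeats all three under its hypotheses, general approach and primary analysis headings, and adds no echo timing of its own.

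**The concern.** Section 8.1 is the text that staff would follow on the day. If they take the echo sentence at face value, two sets of data are never collected: a pre-cannabis scan at any cannabis visit, and a post-exercise scan without cannabis. A scan not taken on the day cannot be recovered later.

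Hypotheses 3 to 6 predict that cardiac measures fall (or do not fall) following a given exposure. Without a same-day baseline, the reference for that change would be the control-visit scan. That visit lies outside the randomised order, because 6.3 randomises only the four experimental visits of a phase. The exposure effect would then be mixed with visit order and day-to-day variation. The exercise condition in the primary analysis would have no cardiac value after exercise at all.

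**Working it through.** **Step 1. Set the time points side by side.**

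| Scan | Required or needed by | Listed for echo in 8.1? |
|---|---|---|
| Before cannabis, each cannabis visit | 4.1 | No |
| After cannabis, each cannabis visit | 4.1, 9.4.2 | Yes |
| Before exercise, control visit | – | Yes |
| After exercise, control visit | 9.1 hypothesis 3, 9.4.1, 9.4.2 | No |

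The first gap contradicts 4.1. The second does not, because the 4.1 sentence concerns consumption and nothing is consumed at Visit 1. It conflicts with 9.1, 9.4.1 and 9.4.2 and with their counterparts in the SAP.

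**Step 2. Distance to the substitute baseline.** Nominal days are from the Schedule of Activities. Visit 1 is Day 7, Phase I visits are Days 14 to 35, and Phase II visits are Days 42 to 63.

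- Phase I: 14 − 7 = 7 to 35 − 7 = 28 days.
- Phase II, for a participant continuing from Phase I with no second control visit: 42 − 7 = 35 to 63 − 7 = 56 days.

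The Phase II gap is conditional. Section 4.1 says each phase requires a control visit, whereas the schedule's footnote asks for one only from people who skipped Phase I.

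**Step 3. Reproduce the planned sample size.** Inputs from 9.2 for "cardiac function (pilot work, peak longitudinal strain": pre −18.3 (SD 1.2), post −17.0 (SD 1.9), 15 participants, power at least 0.8, alpha 0.05. Tests are two-sided (9.4.1). The pre/post correlation r is not given, so it is an assumption here.

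- Change: 18.3 − 17.0 = 1.3.
- SD of change = √(s₁² + s₂² − 2·r·s₁·s₂) = √(1.44 + 3.61 − 4.56·r).
- At r = 0.5: √(5.05 − 2.28) = √2.77 = 1.664, and the standardised change is 1.3 / 1.664 = 0.781.
- Paired t-test, noncentral t with 14 degrees of freedom: power 0.803 at n = 15, the smallest n to reach 0.80.

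The planned 15 is therefore reproduced from strain if r = 0.5.

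**Step 4. Vary r.** If the baseline comes from another day, the relevant r is a between-visit correlation, also not given.

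| Assumed r | SD of change | Power, n = 15 | Power, n = 20 | n for 80% |
|---|---|---|---|---|
| 0 (extreme) | 2.247 | 0.550 | 0.690 | 26 |
| 0.2 | 2.034 | 0.634 | 0.774 | 22 |
| 0.3 | 1.919 | 0.685 | 0.820 | 20 |
| 0.4 | 1.796 | 0.741 | 0.866 | 18 |
| 0.5 | 1.664 | 0.803 | 0.912 | 15 |
| 0.7 | 1.363 | 0.929 | 0.981 | 11 |

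The n = 20 column applies only if everyone recruited to a phase completes it. No value of n supplies the missing post-exercise control scan.

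**Step 5. Does strain set n = 15?** Not demonstrably. The same test also returns 15 from the exercise flow-mediated dilation figures at r of about 0.22 to 0.28, and from the pulse wave velocity figures at r of about 0.05 to 0.11. Strain is the limiting endpoint only if one r is assumed for all.

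**The case against.** The best defence is that the echo sentence is incomplete drafting, not a decision to omit scans. It does not say echo is confined to those times, whereas the nerve-activity bullet just above it does use a word of restriction. Read together, 4.1 and 9.4.2 already call for the scans missing from 8.1. The schema, captioned as showing the schedule of measures, is not visible in the text reviewed and may give timing within visits. All of this stands as a reason to call the point an inconsistency and not a design choice. It does not remove the conflict: the two neighbouring bullets on pulse wave velocity and flow-mediated dilation state both time points and the echo bullet does not, so staff could reasonably follow either text.

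A reader might also infer that the cardiac hypotheses lose every valid comparison. The documents do not support that. Smoking versus vaporizing and THC versus CBD can still be compared on post-consumption values within participant, in randomised order, with no same-day baseline, and Section 3 gives those contrasts particular emphasis.

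Nor do the documents support quoting power of 0.55, or a need for 26 participants, as the consequence. Those figures require r = 0, meaning that two scans of one person are no more alike than scans of two different people. Section 4.2 justifies the within-subject design by variation between individuals (chiefly for pulse wave velocity and flow-mediated dilation), which points towards positive correlation.

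**Conclusion.** The point holds as an internal contradiction with a lasting consequence if 8.1 is followed literally. It rests on reading 8.1's specific echo timings as complete, which is an inference, though a fair one given the bullets around it.

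- **Certain from the text:** 8.1 and 4.1 disagree on the pre-consumption scan, and 8.1 lists no post-exercise control scan although 9.1, 9.4.1 and 9.4.2 (and the SAP) need one.
- **Follows if 8.1 governs:** change from baseline in hypotheses 3 to 6, which is 4 of 8 primary hypotheses, would use a non-randomised scan taken at least 7 nominal days earlier. The cardiac effect of exercise alone could not be estimated.
- **Conditional:** the power loss. With a between-visit r of 0.2 to 0.4, power for strain at n = 15 would be 0.63 to 0.74. At r of 0.5 or more the planned 15 still suffices.

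**What to change.** Amend 8.1 and the Schedule of Activities to state echocardiography before and after consumption at every cannabis visit, and before and after exercise at the control visit, in line with 4.1 and 9.4.2. In the same edit, say whether the post-cannabis scan at the combined visits comes before exercise, after it, or both, since 8.1 is silent. Describe the stress echocardiography that the schedule marks at Visits 2, 4, 6 and 8, which 8.1 does not mention. Settle whether Phase II participants who continue from Phase I repeat the control visit.

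In 9.4.2 and the SAP, define the baseline for each cardiac measure as that visit's pre-exposure scan, and analyse the post value adjusted for it. The covariates now named there (heart rate, blood pressure, pulse wave velocity) do not include it.

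Cost: one further scan per visit. That is 4 cannabis visits + 1 control visit = 5 per participant per phase, or 5 × 20 = 100 scans per phase at full recruitment (fewer if continuing participants do not repeat the control visit). Four of the five are already required by 4.1. A combined visit scanned after both consumption and exercise would add to this. No new visits or equipment are needed, but each visit becomes longer.

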## 8.2 SAFETY AND OTHER ASSESSMENTS

The two screening procedures (Eligibility Questionnaire, PARQ+) will be implemented in order to ensure that only participants who are fit to exercise, and who possess no characteristics that contraindicate medicinal cannabis use will be included in the study. As previously mentioned, each of these questionnaires will attempt to identify specific characteristics that suggest that study inclusion would not be recommended for a given individual.

Participant safety will be monitored throughout each study visit via investigator supervision of study procedures, monitoring of vital signs, electrocardiogram, imaging assessments, and questionnaires. Additionally, adverse events will be recorded throughout each study visit in detail, should they occur.

Upon arrival to the laboratory participants will have their seated blood pressure measured prior to each incidence of cannabis consumption or exercise. Participants must fall in the

normotensive range in order for continuation of study procedures. Blood pressure and heart rate will be recorded throughout all study procedures following cannabis consumption. Additionally, participant's heart rate will be monitored via electrocardiogram. Digital electrocardiographic measures will not be analyzed following study visits; however, it will be monitored during each study visit. In the event of electrocardiographic abnormalities, study procedures will be halted. If electrocardiogram abnormalities are detected and medical attention is necessary, emergency services will be immediately contacted. The principal investigator will be responsible for monitoring for electrocardiogram abnormalities. The principal investigator is trained to do so through his certification as a Certified Exercise Physiologist, accredited by the Canadian Society for Exercise Physiology.

In the assessment of certain primary endpoints, ultrasound imaging of the brachial artery and the heart will occur. If any vascular or cardiac abnormalities become evident to investigators, then emergency services will be contacted, if necessary. As the investigators performing these measures are not physicians, they will not attempt any further specialized imaging, or provide a diagnosis to the participant.

Throughout each smoking protocol, a member of the investigatory team will supervise participants to ensure maximal adherence. If the participant engages in behaviors that are likely to augment the cannabis dosage, such as prolonged breath holding, they will be instructed to cease such behaviors. This investigator supervision will ensure that participants are receiving the desired dose of cannabis.

After completion of study procedures, participants will be required to remain in the laboratory for a period of 4 hours beginning from the end of the cannabis inhalation procedure. This period of monitored recovery has been implemented in an effort to minimize the subjective effects of cannabis experienced by participants prior to their release from the laboratory. In addition, participants will be required to complete the drug effects questionnaire each hour following the completion of study procedures. This questionnaire will evaluate the extent to which participants are experiencing the subjective effects of cannabis. If participants indicate that they are still experiencing subjective effects at the end of the 4-hour recovery period via the DEQ, they will be required to remain until effects have subsided. Blood pressure and heart rate will also be monitored throughout the recovery period. Measurements will be taken each hour with the administration of the DEQ.

